4.2.2 Study Group 2 (Chronic Pain in MS): Study Endpoints

Primary study endpoint will be change in the Patient Reported Outcomes Measurement Information System (PROMIS) pain intensity and interference measures administered at baseline, treatment end, and study end.

Secondary outcomes will include additional measures of pain and other symptoms (i.e. mood and fatigue). We will also measure the acute effects of the treatment on pain before and after each VR session.

5 Study Enrollment and Withdrawal

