7.1 Study Procedures/Evaluations

Participants will complete an informed consent form before any study procedures begin. Participants under the age of 18 will complete an assent form while their legal parent or guardian will complete a consent form.

Participants will complete relevant assessments listed in [Table 2](#) before undergoing a VR session.

Participants may complete as much as one hour of VR therapy during any given session.

Study Group 1: There may be as many as twelve VR sessions during the course of the study. Study personnel will be available to guide participants during the entire duration of the VR session and ensure each session is completed safely. VR treatment will entail use of computer software designed to immerse participants and engage them in exercises. Software includes virtual painting, walking through vivid and calming settings, solving puzzles, among others.

Study Group 2: Similar to study group 1, study personnel will be available to guide participants throughout each VR session. VR treatment will be identical to study group 1.

Participants with MS will only be able to receive eight treatment sessions in this study group and will complete their treatment over four weeks.

Two treatments sessions must be completed each week (of the four weeks) and separated by at least one day. For example, if a participant completes one of their weekly treatments on Monday, they are not able to complete the treatment on Tuesday but may come in on any of the remaining weekdays that study staff are available.

Participants will attend a baseline visit with assessment and training procedures and receive their first treatment immediately after all baseline assessments. Participants will then complete the remaining seven treatment sessions over four weeks. At the final treatment session, participants will repeat assessments. One week following the final treatment session, participants will be asked to return to clinic to complete assessments once more to test cumulative benefits one week following treatment end.

CONFIDENTIAL

This material is the property of the NYU School of Medicine and Langone Medical Center. Do not disclose or use except as authorized in writing by the study sponsor

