Primary outcome will be the change in PROMIS Pain interference from baseline to the study end visit. Based on a previous, successful clinical trial in chronic pain also using an 8-session nonpharmacologic intervention[20], we can expect to have 89% power to detect a significant group difference between the two study conditions. We will also compare change between the groups from baseline to treatment end on the additional self-report measures.

Secondary outcomes will be change in pain visual analog scales completed before and after each session to evaluate acute treatment effects and changes in medication usage from baseline to treatment end measured qualitatively[21]. We will also analyze pain before and after each VR session with the Wong-Baker Faces Pain Rating Scale to compare the immediate analgesic effects of each condition and this cumulative change across sessions.

10 Source Documents and Access to Source Data/Documents

Data will be entered in the HIPAA-compliant NYU REDCap database designed specifically for this study. An anonymous database number will be assigned to each participant and will be used for both the Data Entry Sheet and the Patient Follow-up Sheets. The original consent, which includes the patient name and ID number, will be stored separately in a locked filing cabinet in a locked office. Access to this data will be restricted to study personnel only. Research data will be entered online through the secure NYU database software REDCap and source documents will be kept in a locked filing cabinet in a locked office. Participant data will be coded by the assigned ID and identifying information will not be presented or published to maintain participant privacy and confidentiality.

11 Quality Assurance and Quality Control

- Development of standard protocols to perform all data collection and follow-up activities.
- Use of standardized forms.
- Uniform criteria for patient recruitment.
- Standardized data processing.
- Regular communications between study staff and study investigators to resolve questions.
- Performance monitoring of data collection and data processing activities, as well as preparation of periodic reports and analyses on performance monitoring.
- Monthly monitoring of recruitment statistics.

12 Ethics/Protection of Human Subjects

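### Section 9 plans no treatment-end comparison of Group 2 pain interference and no study-end comparison of the additional self-report measures, and leaves a missed last visit unaddressed; one longitudinal model would cover these gaps

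*Combined protocol and SAP*

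**What the plan says.** Section 4.2.2 makes PROMIS pain intensity and interference the Group 2 primary endpoint, "administered at baseline, treatment end, and study end". Section 7.1 sets up the last two of these occasions. First: "At the final treatment session, participants will repeat assessments". Then, at a separate visit, "participants will be asked to return to clinic to complete assessments once more to test cumulative benefits one week following treatment end". Table 3 in Section 7.2 schedules most measures at the final visit and marks a number of them as required for Group 2.

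Section 9 is narrower. On the primary: "Primary outcome will be the change in PROMIS Pain interference from baseline to the study end visit". On the rest: "We will also compare change between the groups from baseline to treatment end on the additional self-report measures". Its secondary outcomes are visual analogue pain scales around each session and "changes in medication usage from baseline to treatment end measured qualitatively". It adds: "We will also analyze pain before and after each VR session with the Wong-Baker Faces Pain Rating Scale", including cumulative change across sessions.

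Section 9 limits the Group 2 analyses to participants with at least 6 of 8 sessions and expects up to 10% dropout from 44, leaving 20 or more per group. It names no test or model for Group 2 and no rule for missing values.

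**The concern.** Two comparisons that the visit schedule supports are not planned: the arm difference in pain interference at treatment end, and the arm difference in the additional self-report measures at study end. Section 7.1 says that the last visit is there to look at benefit one week on, yet Section 9 uses it for one measure only. Whether an effect on a given measure persists over that week therefore has no planned same-measure comparison. With two time points collected and no model named, the choice of time point could also be made after the results are seen.

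The second issue is attendance. Study end is a return visit without a VR session. Someone can meet the 6-of-8 rule, provide treatment-end data and have no study-end value, in which case the primary change cannot be calculated directly. If people who had not improved by treatment end skip that visit more often in one arm, a comparison of those who attended is tilted towards that arm, even though the treatment-end value that predicts absence was collected.

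**Working it through.** **Time points, side by side (Group 2)**

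| Measure | Collected | Compared between arms in Section 9 |
|---|---|---|
| PROMIS Pain Interference | baseline, treatment end, study end (4.2.2) | study end |
| Additional self-report measures | repeated at final session and one week later (7.1; Table 3) | treatment end |
| Session pain ratings | before and after each session | each session, and cumulatively |

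**The plan's own figures.** Completers: 44 × 0.9 = 39.6, or 19.8 per arm, which rounds to the stated 20. The 89% power cannot be reproduced because effect size, SD, alpha and test are not given. Solving backwards with two-sided 0.05, a t-test and 20 per arm (all but the 20 assumed), 89% implies a standardised difference of about 1.03.

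**Power if study-end values are missing at random.** Hold d = 1.03. With m of n = 20 per arm missing, a longitudinal model has effective size n_eff = (n − m) / (1 − ρ² × m/n), where ρ is the correlation between change to treatment end and change to study end, assumed 0.5 to 0.8. For m = 2 and ρ = 0.7: 18 / (1 − 0.49 × 0.1) = 18.93.

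| Missing per arm | Dropped | Longitudinal model |
|---|---|---|
| 0 | 89.0% | – |
| 2 | 85.4% | 86.3% to 87.7% |
| 4 | 80.8% | 82.9% to 86.1% |

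**Standard error of the arm difference.** Assumed correlations: 0.5 between baseline and each later visit, 0.7 between treatment end and study end. Unit: the SD of a single visit's score. With 10% missing at random, 18 per arm have study-end values.

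- Change score: variance 2 × (1 − 0.5) = 1, so SE = √(2 × 1/18) = 0.333.
- Baseline-adjusted, attenders only: variance 1 − 0.5² = 0.75, so SE = √(2 × 0.75/18) = 0.289.
- Longitudinal model: correlation of the two later visits given baseline = (0.7 − 0.25)/0.75 = 0.6; n_eff = 18/(1 − 0.36 × 0.1) = 18.67; SE = √(2 × 0.75/18.67) = 0.283.

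Simulation (20,000 replicates, 20 per arm) gives slightly larger small-sample values: about 0.335, 0.295 and 0.290. Most of the gain comes from baseline adjustment and little from the treatment-end data.

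**Bias.** Same correlations, no true effect. A non-improver is someone with no fall from baseline at treatment end, which is half of participants on average. If 40% of non-improvers in one arm miss study end, 0.4 × 0.5 = 20% of that arm is missing, or 10% overall.

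| Non-improvers missing study end, by arm | Bias, change score in attenders (SD) | Rejection of a true null, nominal 5% |
|---|---|---|
| 40% vs 0% | about 0.14 | 6.9% |
| 30% vs 10% | 0.07 | 5.2% to 5.3% |
| 20% vs 0% | 0.06 | 5.2% to 5.4% |
| 20% vs 20% | 0.00 | about 5% |

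The bias favours the arm that loses more non-improvers. In the 40% versus 0% case, baseline adjustment in attenders alone still leaves about 0.09 SD; the longitudinal model leaves 0.00.

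**The case against.** A reader might infer that a missed last visit removes the participant from the primary analysis. The documents do not say so. Section 9 names no Group 2 model and no missing-data method, and its inclusion rule depends on sessions completed, not on attendance at study end. What can be said is that the handling is unspecified, and that a plain change score would have no value for that person. The bias figures rest on that assumed method.

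A reader might also infer that the data collected during treatment go unused. They do not: pain is analysed around every session and cumulatively. The gap is confined to the two contrasts named above.

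Nor does the difference in timing stop the secondary results from supporting the primary. The two occasions are one week apart, naming a single primary time point is good practice, and end-of-treatment secondaries can reasonably accompany it.

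The size is also open to challenge. Nothing in the documents suggests attendance as lopsided as 40% versus 0%: both arms receive VR and participants are blinded to catalogue. Even then the bias is 0.14/1.03, about 14% of the effect implied by the stated power, and 0.14/0.335, about 0.4 of a standard error. The model is unbiased in the simulation because absence was generated from values that it includes. It helps only those with treatment-end data, and earlier dropouts gain nothing. Reporting about eight required self-report or pain-rating measures at two visits gives about 16 contrasts in some 40 people.

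All of this stands as a limit on size and wording. It does not supply the missing contrasts or say how a missing study-end value will be handled.

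**Conclusion.** The point holds in a limited form. Section 9 plans no treatment-end contrast for pain interference and no study-end contrast for the additional self-report measures, although both are collected, and it does not match the time points in Section 4.2.2. It is also silent on a participant with 6 or more sessions and no study-end value.

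No stated figure in the documents is contradicted. Under the assumed correlations, the better analysis lowers the standard error from about 0.34 to 0.29 SD, mainly by adjusting for baseline. The bias avoided lies between 0 and about 0.14 SD, depending on how unequally non-improvers miss the last visit. Power recovered under random absence is modest, about 1 to 5 points. The stronger readings, that absentees are certainly dropped or that the secondary results cannot support the primary, are not supported. The main gains are a primary result that depends less on who returns for the last visit, and time points fixed in advance.

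**What to change.** In Section 9, analyse Group 2 PROMIS Pain Interference with one baseline-adjusted longitudinal model (arm by visit, unstructured covariance) that includes treatment-end and study-end values. Make the study-end arm difference the single primary contrast and state missing at random as the assumption. State how participants who meet the session rule but lack a study-end value enter the analysis.

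Report the treatment-end contrast for pain interference as secondary. Report the additional measures at both visits as secondary or exploratory, without a confirmatory claim, so that the extra contrasts do not create a multiplicity problem. Align Sections 4.2.2 and 9 on measures and time points.

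The cost is revised wording, slightly more analysis and more secondary contrasts to report. No new visits, data or participants are needed. The change does not alter the 6-of-8-session rule and does not help participants without treatment-end data.

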12.1 Ethical Standard

The investigator will ensure that this study is conducted in full conformity with Regulations for the Protection of Human Subjects of Research codified in 45 CFR Part 46, 21 CFR Part 50, 21 CFR Part 56, and/or the ICH E6.

12.2 Institutional Review Board

The protocol, informed consent form(s), recruitment materials, and all participant materials will be submitted to the IRB for review and approval. Approval of both the protocol and the consent form must be obtained before any participant is enrolled. Any amendment to the protocol will require review and approval by the IRB before the changes are implemented to the study. All changes to the consent form will be IRB approved; a determination will be made regarding whether previously consented participants need to be re-consented.

12.3 Informed Consent Process

All potential participants will complete a screening interview to ensure general eligibility. The study staff member speaking to the subject will provide the subject with an overview of the study and verbally receive their permission, under a waiver of documentation of consent, to complete the general eligibility screening. The pre-

CONFIDENTIAL

This material is the property of the NYU School of Medicine and Langone Medical Center. Do not disclose or use except as authorized in writing by the study sponsor

screening measures will inquire into demographic background, any auditory, visual, or motor impairment, disclosure of neurological disorder, and current medication use. This phone screen is minimal risk to the participant and collected information will be maintained in secured, locked files. De-identified information (assigned a study screening code) will be entered into a secure, NYU approved online screening database. If a participant is not eligible, they will be considered a screen fail. No additional information will be collected. PHI will be destroyed immediately if a participant is not eligible or does not return to sign written consent/authorization to participate. Only study staff will have access to these records. Once the participant is generally eligible, the PI, or one of the trained study team members will review the consent form with the subject and explain the purpose of the study, the procedures, as well as risks and benefits. All questions will be addressed before acquiring the participant's signed consent. Subjects must have capacity to consent in order to be enrolled in the study. Referring clinicians and NYU clinicians doing the medical screening will be responsible for assessing the capacity to consent. An independent assessor will not be utilized.

12.3.1 Consent/Assent and Other Informational Documents Provided to Participants

Consent forms describing in detail the study agent, study procedures, and risks are given to the participant and written documentation of informed consent is required prior to starting intervention/administering study product. The following consent materials are submitted with this protocol

- *Study Consent (Adult and Pediatrics)*
- *Study Assents (12-14 and 15-17)*

12.3.2 Consent Procedures and Documentation

Subjects who are eligible for this study and are over 18 years of age will be asked, following an appropriate discussion of risks and benefits, to give consent to the study for further study procedures. When a minor who was previously enrolled in the study through parental or a guardian's consent and participant assent turns 18 years of age, they will complete a new consent form for adults (they will not require parental or guardian signature as an adult) before the completion of any further study procedures.

Parental Permission: A portion of subjects who are eligible for this study are under 18 years of age, and written permission from parents or legal guardians will be required for participation. After determining that a subject is eligible, the site investigator or designee will approach the parent or legal guardian to offer participation for their child in the study. The parent or legal guardian will be informed about the objectives of the study and the potential risks and benefits of participation. If the parent or legal guardian refuses permission for their child to participate, then all clinical management will be provided by the clinical staff in accordance with institutional practice and judgment.

Child Assent: Children will be asked, following an age-appropriate discussion of risks and benefits, to give assent to the study or further study procedures.

Subject Capacity: All participants will be confirmed to have the capacity to provide consent by a member of the core physician group as described above. Any participants that could minimally meet the criteria for cognitive impairment will not be enrolled into the study.

Debriefing Procedures: No information will be purposely withheld from the subjects. A clinical neuropsychologist (PI) and the treatment team will be available to answer any questions concerning the tests and results that may arise. An enrollment log will be maintained and consent and assent forms will be kept in secure location separate from the participant's data.

After review of the consent or assent form and prior to the start of the first session, the PI or one of the trained study staff members will obtain written consent or assent with a signature of the patient on the consent or assent form. All original signed consent forms will be maintained in the study file, separate from the participant data.

CONFIDENTIAL

12.4 Participant and Data Confidentiality

Information about study subjects will be kept confidential and managed according to the requirements of the Health Insurance Portability and Accountability Act of 1996 (HIPAA). Those regulations require a signed subject authorization informing the subject of the following:

- What protected health information (PHI) will be collected from subjects in this study
- Who will have access to that information and why
- Who will use or disclose that information
- The rights of a research subject to revoke their authorization for use of their PHI.

In the event that a subject revokes authorization to collect or use PHI, the investigator, by regulation, retains the ability to use all information collected prior to the revocation of subject authorization. For subjects that have revoked authorization to collect or use PHI, attempts should be made to obtain permission to collect at least vital status (i.e. that the subject is alive) at the end of their scheduled study period.

Participant confidentiality is strictly held in trust by the participating investigators, their staff, and the sponsor(s) and their agents. Therefore, the study protocol, documentation, data, and all other information generated will be held in strict confidence. No information concerning the study or the data will be released to any unauthorized third party without prior written approval of the sponsor.

The study monitor, other authorized representatives of the sponsor, representatives of the IRB or pharmaceutical company supplying study product may inspect all documents and records required to be maintained by the investigator, including but not limited to, medical records (office, clinic, or hospital) and pharmacy records for the participants in this study. The clinical study site will permit access to such records.

The study participant's contact information will be securely stored at each clinical site for internal use during the study. At the end of the study, all records will continue to be kept in a secure location for as long a period as dictated by local IRB and Institutional regulations.

Study participant research data, which is for purposes of statistical analysis and scientific reporting, will be transmitted to and stored at NYU Langone Medical Center. This will not include the participant's contact or identifying information. Rather, individual participants and their research data will be identified by a unique study identification number. The study data entry and study management systems used by clinical sites and by NYU Langone Medical Center research staff will be secured and password protected. At the end of the study, all study databases will be de-identified and archived at the NYU Langone Medical Center.

13 Data Handling and Record Keeping

13.1 Data Collection and Management Responsibilities

Paper and computerized data will be collected. Data will be entered in the HIPAA-compliant NYU REDCap database designed specifically for this study.

13.2 Study Records Retention

Study documents will be retained for the longer of 3 years after close-out, 5 years after final reporting/publication, or 2 years after the last approval of a marketing application is approved for the drug for the indication for which it is being investigated or 2 years after the investigation is discontinued and FDA is notified if no application is to be filed or if the application has not been approved for such indication. No records will be destroyed without the written consent of the sponsor, if applicable. It is the responsibility of the sponsor to inform the investigator when these documents no longer need to be retained.

13.3 Protocol Deviations

All protocol deviations will be addressed in study source documents and reported to the IRB.

CONFIDENTIAL

This material is the property of the NYU School of Medicine and Langone Medical Center. Do not disclose or use except as authorized in writing by the study sponsor

13.4 Publication and Data Sharing Policy

This study will comply with the NIH Public Access Policy, which ensures that the public has access to the published results of NIH funded research. It requires scientists to submit final peer-reviewed journal manuscripts that arise from NIH funds to the digital archive PubMed Central upon acceptance for publication.

The International Committee of Medical Journal Editors (ICMJE) member journals have adopted a clinical trials registration policy as a condition for publication. The ICMJE defines a clinical trial as any research project that prospectively assigns human subjects to intervention or concurrent comparison or control groups to study the cause-and-effect relationship between a medical intervention and a health outcome. Medical interventions include drugs, surgical procedures, devices, behavioral treatments, process-of-care changes, and the like. Health outcomes include any biomedical or health-related measures obtained in patients or participants, including pharmacokinetic measures and adverse events. The ICMJE policy, and the Section 801 of the Food and Drug Administration Amendments Act of 2007, requires that all clinical trials be registered in a public trials registry such as ClinicalTrials.gov, which is sponsored by the National Library of Medicine. Other biomedical journals are considering adopting similar policies. For interventional clinical trials performed under NIH IC grants and cooperative agreements, it is the grantee's responsibility to register the trial in an acceptable registry, so the research results may be considered for publication in ICMJE member journals. The ICMJE does not review specific studies to determine whether registration is necessary; instead, the committee recommends that researchers who have questions about the need to register err on the side of registration or consult the editorial office of the journal in which they wish to publish.

FDAAA mandates that a "responsible party" (i.e., the sponsor or designated principal investigator) register and report results of certain "applicable clinical trials":

- Trials of Drugs and Biologics: Controlled, clinical investigations, other than Phase I investigations of a product subject to FDA regulation;
- Trials of Devices: Controlled trials with health outcomes of a product subject to FDA regulation (other than small feasibility studies) and pediatric post market surveillance studies.
- NIH grantees must take specific steps to ensure compliance with NIH implementation of FDAAA.

14 Study Finances

